## Definition of Cardiovascular Events

Cardiovascular Events (CV) Definition:

Investigators will be required to fill out the specific CV event page of the CRF for the following AEs and SAEs:
 
 
• Myocardial infarction/unstable angina
 
• Congestive heart failure
 
• Arrhythmias
 
• Valvulopathy
 
• Pulmonary hypertension
 
• Cerebrovascular events/stroke and transient ischemic attack
 
• Peripheral arterial thromboembolism
 
• Deep venous thrombosis/pulmonary embolism
 
• Revascularization
 

## Recording AE and SAE

AE and SAE Recording

 
• When an AE/SAE occurs, it is the responsibility of the Investigator to review all documentation (eg, hospital progress notes, laboratory, and diagnostics reports) related to the event.
 
• The Investigator will then record all relevant AE/SAE information in the CRF.
 
• It is not acceptable for the investigator to send photocopies of the participant's medical records to GSK in lieu of completion of the GSK /AE/SAE CRF page.
 
• There may be instances when copies of medical records for certain cases are requested by GSK. In this case, all participant identifiers, with the exception of the participant number, will be redacted on the copies of the medical records before submission to GSK.
 
• The Investigator will attempt to establish a diagnosis of the event based on signs, symptoms, and/or other clinical information. Whenever possible, the diagnosis (not the individual signs/symptoms) will be documented as the AE/SAE.
 

Assessment of Intensity

The investigator will make an assessment of intensity for each AE and SAE reported during the study and assign it to categories according to the definitions in CTCAE v5.0.
 
An event is defined as 'serious' when it meets at least 1 of the predefined outcomes as described in the definition of an SAE.

Assessment of Causality

 
• The Investigator is obligated to assess the relationship between study treatment and each occurrence of each AE/SAE.
 
• A "reasonable possibility" of a relationship conveys that there are facts, evidence, and/or arguments to suggest a causal relationship, rather than a relationship cannot be ruled out.
 
• The Investigator will use clinical judgment to determine the relationship.
 
• Alternative causes, such as underlying disease(s), concomitant therapy, and other risk factors, as well as the temporal relationship of the event to study treatment administration will be considered and investigated.
 
• The Investigator will also consult the Investigator's Brochure (IB) and/or Product Information, for marketed products, in his/her assessment.
 
• For each AE/SAE, the Investigator must document in the medical notes that he/she has reviewed the AE/SAE and has provided an assessment of causality.
 
• There may be situations in which an SAE has occurred and the investigator has minimal information to include in the initial report to GSK. However, it is very
 

**important that the investigator always make an assessment of causality for every event before the initial transmission of the SAE data to GSK.**

- The Investigator may change his/her opinion of causality in light of follow-up information and send an SAE follow-up report with the updated causality assessment.
- The causality assessment is one of the criteria used when determining regulatory reporting requirements.

#### **Follow-up of AE and SAE**

- The Investigator is obligated to perform or arrange for the conduct of supplemental measurements and/or evaluations as medically indicated or as requested by GSK to elucidate the nature and/or causality of the AE or SAE as fully as possible. This may include additional laboratory tests or investigations, histopathological examinations, or consultation with other health care professionals.
- If a participant dies during participation in the study or during a recognized follow-up period, the investigator will provide GSK with a copy of any post-mortem findings including histopathology.
- New or updated information will be recorded in the originally completed CRF.
- The Investigator will submit any updated SAE data to GSK within 24 hours of receipt of the information.

#### **Reporting of SAE to GSK**

##### **SAE Reporting to GSK via Electronic Data Collection Tool**

- The primary mechanism for reporting SAE to GSK will be the electronic data collection tool.
- If the electronic system is unavailable, then the site will use the paper SAE data collection tool (see next section) in order to report the event within 24 hours.
- The site will enter the SAE data into the electronic system as soon as it becomes available.
- The Investigator or medically-qualified sub-investigator must show evidence within the eCRF (e.g., check review box, signature, etc.) of review and verification of the relationship of each SAE to IP/study participation (causality) within 72 hours of SAE entry into the eCRF.
- After the study is completed at a given site, the electronic data collection tool will be taken off-line to prevent the entry of new data or changes to existing data.
- If a site receives a report of a new SAE from a study participant or receives updated data on a previously reported SAE after the electronic data collection tool has been taken off-line, then the site can report this information on a paper SAE form (see next section) or to the medical monitor by telephone.

- Contacts for SAE reporting can be found in the SRM.

#### **SAE Reporting to GSK via Paper CRF**

- Email facsimile transmission of the SAE paper CRF is the preferred method to transmit this information to the medical monitor.
- In rare circumstances and in the absence of facsimile/email capability, notification by telephone is acceptable with a copy of the SAE data collection tool sent by overnight mail or courier service.
- Initial notification via telephone does not replace the need for the Investigator to complete and sign the SAE CRF pages within the designated reporting time frames.
- Contacts for SAE reporting can be found in the SRM.

## 13.6. Appendix 6: Contraceptive Guidance and Collection of Pregnancy Information

### Contraception Guidance

#### Male participants

- Male participants with female partners of child-bearing potential are eligible to participate if they agree to ONE of the following:
  - Are abstinent from penile-vaginal intercourse as their usual and preferred lifestyle (abstinent on a long term and persistent basis) and agree to remain abstinent for a period of 90 days after the last dose of study medication (one spermatogenesis cycle).
  - Agree to use a male condom plus an additional method of contraception with a failure rate of <1% per year as described in [Table 3](#) when having penile-vaginal intercourse with a woman of childbearing potential, for a period of 90 days after the last dose of study medication.
- Men with a pregnant or breastfeeding partner must agree to remain abstinent from penile-vaginal intercourse or use a male condom during each episode of penile penetration during the treatment period and for 6 days after (five terminal half-lives).
- In addition, male participants must refrain from donating sperm during the treatment period and for 90 days after (one spermatogenesis cycle).

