
Teratogenicity of GSK3036656
	
Non-clinical safety
 
Preliminary results from the definitive rat embryo-fetal toxicology are as follows:
 
60mg/kg/day: Reductions in fetal viability and reduced fetal weights, with minimal reductions in
	
Women will be excluded from recruitment to this study.

Potential Risk of Clinical Significance	Summary of Data/Rationale for Risk	Mitigation Strategy
	
body weight gains and malformations including ventricular septal defects (13 animals across 8 litters) and cleft palates (10 animals/6 litters).
 
20mg/kg/day: Reduced fetal weights and incidences of ventricular septal defects (2 animals across 2 litters) that were outside the historical control data in the absence of any maternal effects.
	

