### 3.3.2. Benefit Assessment

Mouse models predict efficacy at human equivalent exposures consistent with the upper doses being tested. Nevertheless, efficacy of GSK3036656 has not been demonstrated in humans and no benefit can be expected from receiving the compound over the 2-week course of the study, and as monotherapy. A significant proportion of people with TB fail treatment (~15% with drug-sensitive up to ~80% with XDR). New effective compounds with novel mechanisms of action are urgently needed for TB, and it is recognised as a priority area by the WHO. The results of this study will establish whether GSK3036656 has activity, tolerability and safety adequate to take into subsequent studies of longer duration with the intention of developing a medicine for TB with a novel mechanism of action that could form part of a new combination treatment regimen for TB.

A delay of treatment with the full standard regimen of 14 days is not expected to have an adverse impact on the ultimate cure of TB in these participants, and this approach has been used as part of recent successful TB drug development programs ([Diacon, 2011b](#), [Diacon, 2013](#)). Participants in this study will have their TB infection carefully characterized and drug sensitivity profiles established.

Participants will remain under constant medical attention and will be housed and monitored in hospital from admission through the duration of the treatment period; this will allow the continuous monitoring of the health conditions of each participant, any of whom can be withdrawn at any stage of the trial and removed from study treatment should his/her condition suggest to the Investigator that this would be in his/her best interest. Multiple blood samples will be taken for safety laboratory studies. Upon discharge, the participants will be given the initial doses of standard TB treatment and immediately referred to the national TB treatment program local TB clinic where they will receive a full course of standard treatment. At the follow-up visit it will be confirmed that this treatment has been initiated and is being continued. The Investigators' primary responsibility is to ensure participant safety.

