## 5.6. Dose Justification

A population pharmacokinetic model was developed based on preliminary concentration-time data obtained in the FTIH study. The model was used to simulate loading and maintenance doses for GSK3036656 based on the EBA study design and accounting for

the effect of renal impairment on exposure (preliminary data suggest GSK303656 is > 70% renally excreted). A target exposure for efficacy of 1.74 ug.h/mL was set based on the exposure associated with efficacy in a mouse infection model and the target attainment rate was defined as the percentage of participants with an AUC0-24 greater than this target exposure. Exposure limits of AUC0-24 of 15 ug.h/mL and Cmax of 1.5 ug/mL were set, based on information in Section 3.3.

A loading dose of GSK3036656 may be administered on the first day (or over multiple days where required in order to not exceed AUC and Cmax exposure limits) of study treatment administration in each cohort. The long half-life of GSK3036656 (45 hours) means that subjects will take up to 10 days to reach steady-state concentrations, which is not optimal for a 14-day treatment study. A loading dose will allow participants to reach steady-state concentrations in 2 to 3 days for a given maintenance dose regimen.

The probability rates for individual participants to exceed GSK3036656 exposure limits and achieve the efficacy target for proposed loading and maintenance dose regimens are shown in Table 1.

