### **Amendment 2 24-SEP-2018**

The primary motivation for this amendment was to update the eligibility criteria to impose a minimum renal function (as defined by creatinine clearance) in light of the first-in-human data that showed the main route of clearance for GSK3036656 is through the kidneys. As a result of the long half-life of GSK3036656, updated dosing strategy has also been implemented incorporating the use of loading doses.

Further changes made to the protocol are detailed in the table below.

Section #	Description of Change	Brief Rationale
Whole document	Minor updates including typographical corrections	Inconsistencies between different parts of the document have been resolved and clarifications inserted where required.
2	Removal of QTc endpoint	The intent of including Holter monitoring assessments in the EBA study was to collect data similar to that obtained in a thorough QT (TQT) study. These data would be used for an exposure-response analysis. However, since a positive control (moxifloxacin) will not be used in the EBA study (as required in a TQT study) and the EBA study is unlikely to achieve maximum concentrations of GSK3036656 that are in the range of 4- to 10-times the therapeutic dose (as required for 1 arm in a TQT study), the decision was made to remove Holter monitoring assessments from the EBA study.
3.3.1	Depigmentation	Depigmentation was seen in some animals in a 4-month GLP toxicology study. The risk-benefit assessment has been updated. Patients with vitiligo will be excluded from the study to avoid confounding in baseline and follow-up skin assessments.
3.3.1	Benefit-risk table - Clinical subsections updated with data from finalised 201040 CSR	Finalised data from the First in Human clinical trial are now available and have been incorporated.
2 & 3.3.1	Cardiac BNP assessment removed	Cardiac BNP is an acute phase reactant and has been reported to be elevated in a wide range of inflammatory conditions. Cardiac BNP monitoring is therefore considered to be of limited value in the context of patients with tuberculosis.

Section #	Description of Change	Brief Rationale
5.6	Loading doses	The long half-life of GSK3036656 means that 6 days are needed to achieve steady state concentrations in blood. The possibility of using loading doses has been included so that steady state may be reached more quickly. A rationale for how doses will be chosen has been included.

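### Appendix 6 prints five terminal half-lives as 6 days, but the only half-life in the protocol (45 hours) makes it 9.4 days

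*Protocol*

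**What the plan says.** The contraception guidance for male participants in Protocol Appendix 6 has separate rules for different partners. Men with a partner of child-bearing potential follow a 90-day rule, and sperm donation is barred for 90 days. Men whose partner is already pregnant or breastfeeding have their own, shorter rule: abstinence or a condom "during the treatment period and for 6 days after (five terminal half-lives").

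Section 5.6 (Dose Justification) gives the half-life: "The long half-life of GSK3036656 (45 hours) means that subjects will take up to 10 days to reach steady-state concentrations". It uses that statement to justify loading doses. Neither document gives any other numeric half-life for GSK3036656, and no separate terminal value appears.

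Two other parts of the protocol bear on the rule. The risk table in Section 3.3.1 lists teratogenicity and reports, for rats at 20 mg/kg/day, "Reduced fetal weights and incidences of ventricular septal defects (2 animals across 2 litters) that were outside the historical control data", without any effect on the mothers; women are excluded as the mitigation. Section 3.3.2 says participants are "housed and monitored in hospital from admission through the duration of the treatment period".

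**The concern.** The rule defines its length by a pharmacokinetic standard, five half-lives, and then prints a number of days. The number does not follow from the half-life in Section 5.6. Both statements are in the current text, so this is not a difference between the amendment history and the protocol as it stands.

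This is an instruction that sites and participants act on, for a drug with a listed teratogenicity risk. Because the men are inpatients during dosing, the post-treatment window is the part of the rule that governs them at home. A man who follows it as printed would stop precautions before five half-lives have passed, if 45 h is right.

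**Working it through.** **Inputs**
- Post-treatment window: 6 days = 6 × 24 = 144 h (Appendix 6).
- Standard claimed for it: five terminal half-lives (Appendix 6).
- Half-life: 45 h (Section 5.6).
- Time to steady state: up to 10 days = 240 h (Section 5.6).
- Last dose: Day 14; follow-up nominally Day 28 (Schedule of Activities).

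**1. Trying to reproduce the 6 days.** Half-life implied = window / 5 = 144 / 5 = 28.8 h. If 6 is rounded from anywhere between 5.5 and 6.5 days, the implied range is 5.5 × 24 / 5 = 26.4 h to 6.5 × 24 / 5 = 31.2 h. Neither document states a half-life in that range, and 45 h lies well outside it. The printed figure is not reproduced, and rounding does not explain it.

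**2. Five half-lives at the stated value.** 5 × 45 h = 225 h; 225 / 24 = 9.375 days, or 10 whole days when rounded up.

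**3. Shortfall.** 225 − 144 = 81 h; 81 / 24 = 3.4 days. In half-lives, the printed window is 144 / 45 = 3.2.

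**4. Drug remaining in the man, assuming mono-exponential decline** (fraction = 0.5^(time / half-life)):

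| Time after last dose | Half-lives at 45 h | Remaining |
|---|---|---|
| 6 days | 3.2 | 0.5^3.2 = 10.9% |
| 9.4 days | 5 | 0.5^5 = 3.1% |
| 10 days | 240 / 45 = 5.33 | 0.5^5.33 = 2.5% |

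**5. Study calendar.** The printed window ends on Day 14 + 6 = Day 20. Five half-lives end on Day 14 + 9.4 = Day 23.4. A 10-day window would end on Day 24.

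**6. Which figure does the current text support?** At 45 h, the 10 days to steady state in Section 5.6 is 5.33 half-lives, or 1 − 0.5^5.33 = 97.5% of steady state, so the two statements in that section agree. At 28.8 h, five half-lives would take only 6 days, and the 10-day statement would not follow. The overdose instruction in Section 9.3, which expects monitoring for at least 14 days until drug is undetectable, also fits slow elimination, though it is weaker evidence.

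**The case against.** The best counter-argument is that the documents show a conflict without proving which side is wrong. Six days is not an isolated slip. The Amendment 2 rationale in Appendix 9 says "The long half-life of GSK3036656 means that 6 days are needed to achieve steady state concentrations in blood", and a sun-exposure restriction deleted in Amendment 3 also equated five half-lives with 6 days. A value near 29 h may once have been in use. On that view the shortfall lies between zero (28.8 h) and 81 h (45 h), and confirming the half-life should come first.

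Part of this stands: the 81 h and the 10.9% depend on 45 h being right. But the support for 6 days as a half-life figure lies in amendment history, which describes superseded text, and the Section 5.6 text recorded for that same Amendment 2 already gives 45 h and up to 10 days. That pattern suggests a figure carried over, although the documents do not confirm it.

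The word terminal in Appendix 6 does not reconcile the figures. No separate terminal value is given, and a terminal half-life would not normally be shorter than the one that governs accumulation.

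Two limits on the consequence also stand. The rat findings come from an embryo-fetal study, not from exposure through a treated male, so they do not show harm between days 6 and 9.4. And because the protocol does not define child-bearing potential, a fertile breastfeeding partner might also fall under the 90-day rule. Even so, these men have a bullet of their own, and a site applying it would stop at 6 days.

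**Conclusion.** The point holds. On the current text, the post-treatment window for men with a pregnant or breastfeeding partner is 3.2 half-lives rather than five: 81 h (3.4 days) short. This rests on the 45 h in Section 5.6, the only half-life stated; the residual percentages also assume mono-exponential decline and describe drug in the man, not exposure of the partner, fetus or infant. The documents do not allow that exposure to be sized. The scope is narrow, with no effect on endpoints, dosing, eligibility or analysis, but a safety instruction carries a number that does not meet its own standard and should be corrected.

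**What to change.** Replace 6 days with 10 days in the pregnant-or-breastfeeding-partner rule in Appendix 6, and in any consent wording that repeats it. The exception is if the sponsor confirms and cites a documented terminal half-life of about 29 h: then 6 days can stay, and the 45 h in Section 5.6 must be corrected, along with the 10-day steady-state statement that depends on it. Either way, one of the two sections has to change.

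The cost is protocol and consent wording plus 10 − 6 = 4 more days of abstinence or condom use for the men concerned. The longer window ends before the nominal Day 28 follow-up and requires no extra visit, sample or change to the analysis.

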**Table 3 Highly Effective Contraceptive Methods**

Highly Effective Contraceptive Methods That Are User Dependent a  Failure rate of <1% per year when used consistently and correctly.

Combined (estrogen- and progestogen-containing) hormonal contraception associated with inhibition of ovulation
 
 
• oral
 
• intravaginal
 
• transdermal
 

Progestogen-only hormonal contraception associated with inhibition of ovulation
 
 
• injectable
 

Highly Effective Methods That Are User Independent

 
• Implantable progestogen-only hormonal contraception associated with inhibition of ovulation
 
• Intrauterine device (IUD)
 
• Intrauterine hormone-releasing system (IUS)
 
• bilateral tubal occlusion
 

Vasectomized partner
 
(A vasectomized partner is a highly effective contraception method provided that the partner is the sole male sexual partner of the WOCBP and the absence of sperm has been confirmed. If not, an additional highly effective method of contraception should be used.)

Sexual abstinence
 
(Sexual abstinence is considered a highly effective method only if defined as refraining from heterosexual intercourse during the entire period of risk associated with the study drug. The reliability of sexual abstinence needs to be evaluated in relation to the duration of the study and the preferred and usual lifestyle of the participant.)

NOTES:

a. Typical use failure rates may differ from those when used consistently and correctly. Use should be consistent with local regulations regarding the use of contraceptive methods for participants in clinical studies.

**Collection of Pregnancy Information**

**Male participants with partners who become pregnant**

- Investigator will attempt to collect pregnancy information on any male participant’s female partner of a male study participant who becomes pregnant while participating in this study. This applies only to participants who receive study treatment.
- After obtaining the necessary signed informed consent from the pregnant female partner directly, the Investigator will record pregnancy information on the

appropriate form and submit it to GSK within 24 hours of learning of the partner's pregnancy.

- Partner will also be followed to determine the outcome of the pregnancy. Information on the status of the mother and child will be forwarded to GSK
- Generally, follow-up will be no longer than 6 to 8 weeks following the estimated delivery date. Any termination of the pregnancy will be reported regardless of fetal status (presence or absence of anomalies) or indication for procedure.

### 13.7. Appendix 7: Liver Safety: Required Actions and Follow-up Assessments

#### Liver chemistry stopping criteria and required follow up assessments

Elevated liver enzymes, transient liver dysfunction, hepatotoxicity and hepatitis are listed as side-effects in the package inserts for Rifafour e-275 (Rifafour, 2002) or equivalent generic alternative, associated with multiple drug components. Therefore, participants allocated to Rifafour e-275 (or equivalent generic alternative) treatment who experience Liver Chemistry Stopping criteria are not mandated in the first instance to undergo those follow-up assessments (which are intended to investigate aetiology). The investigations may still be performed, if required in the judgement of the investigator.

Liver Chemistry Stopping Criteria	
ALT-absolute	ALT $\geq$ 5xULN
ALT Increase	ALT $\geq$ 3xULN persists for $\geq$ 4 weeks
Bilirubin	ALT $\geq$ 3xULN and bilirubin $\geq$ 2xULN (>35% direct bilirubin)
INR^2	ALT $\geq$ 3xULN and INR>1.5, if INR measured
Cannot Monitor	ALT $\geq$ 3xULN and cannot be monitored weekly for 4 weeks
Symptomatic	ALT $\geq$ 3xULN associated with symptoms (new or worsening) believed to be related to liver injury or hypersensitivity
Required Actions and Follow up Assessments	
Actions	Follow Up Assessments

 
• Immediately discontinue study treatment
 
• Report the event to GSK within 24 hours
 
• Complete the liver event CRF and complete an SAE data collection tool if the event also meets the criteria for an SAE
 
• Perform liver chemistry event follow up assessments
 
• Monitor the participant until liver chemistries resolve, stabilize, or return to within baseline (see MONITORING below)
 
• Do not restart/rechallenge participant with study treatment unless allowed per protocol
 
	
For all study participants:
 
 
• Obtain INR and recheck with each liver chemistry assessment until the transaminases values show downward trend
 
• Record the appearance or worsening of clinical symptoms of liver injury, or hypersensitivity, on the AE report form
 
• Record use of concomitant medications on the concomitant medications report form including acetaminophen, herbal remedies, other over the counter medications.
 



and GSK Medical Governance approval is granted (see below)
 
 
• If restart/rechallenge not allowed per protocol or not granted, permanently discontinue study treatment and continue participant in the study for any protocol specified follow up assessments
 
 
MONITORING:
 
For bilirubin or INR criteria:
 
 
• Repeat liver chemistries (include ALT, AST, alkaline phosphatase, bilirubin) and perform liver event follow up assessments within 24 hrs
 
• Monitor participants twice weekly until liver chemistries resolve, stabilize or return to within baseline
 
• A specialist or hepatology consultation is recommended
 
 
For All other criteria:
 
 
• Repeat liver chemistries (include ALT, AST, alkaline phosphatase, bilirubin) and perform liver event follow up assessments within 24-72 hrs
 
• Monitor participants weekly until liver chemistries resolve, stabilize or return to within baseline
 
	
 
• Record alcohol use on the liver event alcohol intake case report form (CRF) page
 
 
For participants on GSK303656 arm
 
 
• Viral hepatitis serology
 
• Obtain blood sample for pharmacokinetic (PK) analysis as soon as possible, and certainly within 14 days after last dose
 
• Serum creatine phosphokinase (CPK) and lactate dehydrogenase (LDH).
 
• Fractionate bilirubin, if total bilirubin <math>\geq 2 \times \text{ULN}</math>
 
• Obtain complete blood count with differential to assess eosinophilia
 
 
For bilirubin or INR criteria:
 
For participants on GSK303656 arm only
 
 
• Auto-immune screen: Anti-nuclear antibody, anti-smooth muscle antibody, Type 1 anti-liver kidney microsomal antibodies, and quantitative total immunoglobulin G (IgG) or gamma globulins.
 
• Serum paracetamol/acetaminophen adduct high performance liquid chromatography (HPLC) assay (quantifies potential acetaminophen contribution to liver injury in participants with definite or likely acetaminophen use in the preceding week [James, 2009]).
 
• Liver imaging (ultrasound, magnetic resonance, or computerised tomography) and /or liver biopsy to evaluate liver
 

---	---

	disease: complete Liver Imaging and/or Liver Biopsy CRF pages.
--	--

1. Serum bilirubin fractionation should be performed if testing is available. If serum bilirubin fractionation is not immediately available, discontinue study treatment for that subject if ALT ≥ 3xULN **and** bilirubin ≥ 2xULN.. Additionally, if serum bilirubin fractionation testing is unavailable, **record presence of detectable urinary bilirubin on dipstick**, indicating direct bilirubin elevations and suggesting liver injury.
2. All events of ALT ≥ 3xULN **and** bilirubin ≥ 2xULN (>35% direct bilirubin) or ALT ≥ 3xULN **and** INR>1.5, if INR measured which may indicate severe liver injury (possible 'Hy's Law'), **must be reported as an SAE (excluding studies of hepatic impairment or cirrhosis)**; INR measurement is not required and the threshold value stated will not apply to participants receiving anticoagulants
3. New or worsening symptoms believed to be related to liver injury (such as fatigue, nausea, vomiting, right upper quadrant pain or tenderness, or jaundice) or believed to be related to hypersensitivity (such as fever, rash or eosinophilia)
4. Includes: Hepatitis A IgM antibody; Hepatitis B surface antigen (HbsAg) and Hepatitis B Core Antibody (IgM); Hepatitis C RNA; Cytomegalovirus IgM antibody; Epstein-Barr viral capsid antigen IgM antibody (or if unavailable, obtain heterophile antibody or monospot testing); Hepatitis E IgM antibody

For PK sampling; record the date/time of the PK blood sample draw and the date/time of the last dose of study treatment prior to PK blood sample draw on the CRF. If the date or time of the last dose is unclear, provide the participant’s best approximation. If the date/time of the last dose cannot be approximated OR a PK sample cannot be collected in the time period indicated above, do not obtain a PK sample. Instructions for sample handling and shipping are in the SRM.

